5.2.2 Secondary outcomes

Mortality at discharge from critical care and at 30 days will be compared between groups using Fisher's exact test. If the number of events allows, logistic regression will be used to compare mortality between groups adjusted for baseline variables.

Mortality at 90 days and at 12 months will be estimated by arm, using Kaplan-Meier methods with patients censored at last available follow-up. If the number of events allows, Cox regression will be used to compare mortality between groups adjusted for baseline variables.

Time to liberation from ventilation will be reported as median time (with 95% confidence interval) by arm, calculated using Kaplan-Meier methods. Unadjusted and adjusted hazard ratios will be calculated using Cox regression. Patients who die on ventilation will be censored at date & time of death.

Duration of organ support to day 30 (calculated as for the primary clinical endpoint) will be compared between groups using a Wilcoxon rank-sum test, in patients stratified by survival status. Duration of organ support by type of support (respiratory invasive; respiratory non-invasive; cardiovascular; renal; other) will be reported by group using medians and interquartile ranges, and counts and percentages of patients ever receiving, but not formally tested for differences between groups. Length of PICU and acute hospital stay will be compared between groups using a Wilcoxon rank-sum test, and reported by group using medians and interquartile ranges, in patients stratified by survival status.

Functional status at PICU discharge will be reported as counts and percentages in each of five possible categories.

All adjusted analysis will include the baseline variables previously listed in section 5.2.1.

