2.3 Sample size

The primary clinical outcome will be analysed using rank-based methods, with death at 30 days ranked as the worst outcome. To achieve 90% power, using simulations based on data from the Oxy-PICU pilot RCT, to detect a clinically meaningful reduction in the mean duration of organ support of 12 hours from 120 to 108 hours and assuming no impact on 7.5% mortality requires a total sample size of 2040 patients (allowing for withdrawal/refusal of deferred consent of 10%).

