5.1.3.3 Time to liberation from ventilation

Liberation from ventilation is defined as the start of a continuous period of at least 48 hours free from ventilation. The time to liberation from ventilation will be measured from randomisation to the start of the first such period.

5.1.3.4 Duration of organ support.

Duration of organ support is defined as for the primary clinical endpoint (number of calendar days from day 1 to 30 on which any support was given).

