5.2.3 Sensitivity analyses

Analysis of the primary clinical endpoint, and relevant secondary endpoints, will be repeated with duration of organ support measured in calendar days from randomisation to the last recorded day of organ support (capped at day 30). Duration of respiratory support will be reported using Kaplan-Meier methods with time measured from randomisation to the end of the last known period of respiratory support which started on or before day 30.

Unadjusted treatment effects for the two components of the composite primary clinical endpoint (days or organ support, and mortality by day 30) will be compared to confirmed that any treatment effect is in the same direction for both components. If this appears not to be the case, the partial proportional odds model⁶ will be used to estimate adjusted treatment effects.

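### Censoring deaths on ventilation makes the Kaplan-Meier median time to liberation too short, and the Cox hazard ratio beside it is not labelled cause-specific

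*SAP*

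**What the plan says.** Section 5.1.3.3 defines the event: "Liberation from ventilation is defined as the start of a continuous period of at least 48 hours free from ventilation". On the time scale it adds: "The time to liberation from ventilation will be measured from randomisation to the start of the first such period".

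Section 5.2.2 gives the analysis: "Time to liberation from ventilation will be reported as median time (with 95% confidence interval) by arm, calculated using Kaplan-Meier methods", followed by "Unadjusted and adjusted hazard ratios will be calculated using Cox regression". The rule for death is one sentence: "Patients who die on ventilation will be censored at date & time of death". The adjusted models take the covariates of section 5.2.1, which include site as a random effect.

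For this outcome the SAP names no cumulative incidence estimate, no subdistribution model, and no rule that counts a child who died as never liberated. Section 5.2.3 adds a related descriptive item, "Duration of respiratory support will be reported using Kaplan-Meier methods", and does not say how deaths enter it.

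Elsewhere death is dealt with explicitly. The primary outcome gives it the worst score, 31 (section 5.1.1). Duration of organ support and length of stay are analysed by survival status (section 5.2.2).

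**The concern.** Censoring is harmless when the censored child could still have had the event later, at the same rate as those who remain at risk. A child who dies on the ventilator cannot be liberated later. One minus Kaplan-Meier with deaths censored therefore estimates liberation as if death did not prevent it. Its median is not the time by which half of the randomised children were liberated, although readers will take it as that.

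The hazard ratio raises a narrower issue. With deaths censored, it compares the rate of liberation among children still alive and ventilated. That is a proper quantity, but the SAP does not name it as such. If the arms differ in deaths on ventilation, the ratio can stay at 1 while a smaller share of one arm is ever liberated.

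There is also a gap in the rule. A child who is extubated and dies within 48 hours has not been liberated under section 5.1.3.3, but did not die on ventilation either. The censoring rule does not cover that child, so the handling would be decided after the data are seen.

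**Working it through.** **The plan's own figures.** The SAP gives no median, event rate or precision for time to liberation, so there is no stated figure to reproduce. The nearest design figures are in section 2.3: an average of 120 h on organ support, to be cut to 108 h, and a death rate of 7.5% taken as equal in both arms. They concern the primary outcome and are borrowed here only for scale.

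**Direction.** Let λ_L(t) and λ_D(t) be the hazards of liberation and of death before liberation, with cumulative hazards Λ_L and Λ_D.

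- Kaplan-Meier with deaths censored: 1 − exp(−Λ_L(t)), which is the integral of λ_L·exp(−Λ_L).
- Actual proportion liberated (cumulative incidence): the integral of λ_L·exp(−Λ_L)·exp(−Λ_D).

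The second integrand is the first times a factor of at most 1. So the Kaplan-Meier curve is never below the true one, and its median is never later. This needs no assumption about the shape of the hazards.

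**Size.** Assumptions, not SAP figures for this outcome: constant hazards; mean time to liberation or death 120 h (borrowed from organ support); share p dying on ventilation from 2.5% to 15%, with 7.5% as the centre (the 30-day mortality in section 2.3, all taken as deaths on ventilation). Then λ_L = (1 − p)/120 and λ_D = p/120, and

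- Kaplan-Meier median = ln 2 / λ_L
- cumulative incidence median = −120 × ln(1 − 0.5/(1 − p))

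At p = 7.5%: ln 2 / (0.925/120) = 89.9 h, against −120 × ln(1 − 0.5/0.925) = 93.3 h. The difference is 3.4 h, or 3.4/93.3 ≈ 4%.

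| Deaths on ventilation | Kaplan-Meier median (h) | Cumulative incidence median (h) | Short by (h) |
|---|---|---|---|
| 2.5% | 85.3 | 86.3 | 1.0 |
| 5% | 87.6 | 89.7 | 2.1 |
| 7.5% | 89.9 | 93.3 | 3.4 |
| 10% | 92.4 | 97.3 | 4.9 |
| 15% | 97.9 | 106.5 | 8.6 |

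**Between arms.** Now hold λ_L at 0.925/120 per hour in both arms and let only deaths on ventilation differ. Set λ_D = λ_L × p/(1 − p) in each arm. The true cause-specific hazard ratio is 1 and the Kaplan-Meier median is 89.9 h in both arms. The hazard ratios below are from a simulation of 30,000 children per arm followed to 720 h. For the subdistribution ratio, deaths are kept in the risk set to 720 h.

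| Deaths on ventilation, by arm | Cumulative incidence median (h) | Liberated by 720 h | Cox HR, deaths censored | Subdistribution HR |
|---|---|---|---|---|
| 6% vs 9% | 92.6 vs 94.1 | 93.7% vs 90.8% | 0.99 | 0.93 |
| 5% vs 10% | 92.1 vs 94.7 | 94.7% vs 89.8% | 0.99 | 0.89 |

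The Cox ratios differ from 1 only by simulation error. Both planned summaries show no difference, while the proportion liberated differs by about 3 and 5 percentage points.

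**The case against.** Much can be said for the plan as written.

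- **The Cox ratio is not an error.** Where weaning is identical in both arms, a ratio of about 1 correctly answers the question about the rate of liberation among children alive and ventilated. The subdistribution ratio moves only because mortality was set to differ, and it mixes mortality with weaning. This stands. It is why the Cox ratio should be kept, not replaced.
- **Excess deaths would be visible elsewhere.** Mortality is reported at PICU discharge, 30 days, 90 days and 12 months. Death is ranked worst in the primary outcome, and section 5.2.3 checks that the two components point the same way. A reader might infer that the plan could conceal harm in the trial as a whole, or that it contradicts its own primary outcome. Neither follows: secondary outcomes that separate duration from death are a coherent choice.
- **A day-30 proportion liberated is not a planned output.** At 7.5% deaths the two curves reach 99.6% and 92.3% by day 30 under the same assumptions. It is tempting to call this a reported overstatement of 7 points, but section 5.2.2 plans medians and hazard ratios. The relevant size is the few hours on the median.
- **With equal mortality, the comparison is little affected.** Section 2.3 assumes no effect on mortality. If hazards are also similar, both medians shift alike. This stands, although each reported median is still too short.
- **Section 5.2.3.** A reader might infer the same fault in the duration of respiratory support. The SAP states no rule for death there, so nothing written can be called wrong.

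None of this makes the Kaplan-Meier median the time by which half of the children were liberated, and none of it places a death shortly after extubation.

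**Conclusion.** The point holds for the median and for the gap in the death rule. The direction is certain: censoring deaths can only raise the liberation curve and bring the median forward. The size is modest, about 3 h at 7.5% deaths on ventilation and about 1 to 9 h over 2.5% to 15%. It rests on constant hazards and a 120 h mean borrowed from organ support. Taking all of the 7.5% mortality as deaths on ventilation is an upper limit at that mortality.

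The hazard ratio is correct but incompletely described. It needs its label and a companion measure that responds to deaths.

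A reader might go further and conclude that an arm with more deaths would look faster to wean. That requires deaths to fall mainly on slow-weaning children, and the SAP gives no figures on this. What can be said is that the planned summaries need not register a difference in deaths on ventilation.

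This is a secondary outcome and the primary analysis is untouched. The change is still worth making, because it alters a figure that will be reported and settles a case that the rule leaves open.

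**What to change.** In section 5.2.2:

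1. Treat any death before 48 hours free of ventilation, on or off the ventilator, as a competing event.
2. Report the cumulative incidence of liberation by arm (Aalen-Johansen), and take the median and its 95% confidence interval from that curve.
3. Keep the unadjusted and adjusted Cox hazard ratios, labelled cause-specific, and report Fine-Gray subdistribution hazard ratios beside them.
4. In the adjusted Fine-Gray model, handle site by clustered standard errors or a similar method, since the random effect in section 5.2.1 does not carry over directly. State this as an exception to the rule that all adjusted analyses use the same covariates in the same form.

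In section 5.2.3, state how deaths enter the duration of respiratory support. If they would otherwise be censored, use the same approach.

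The cost is SAP wording. No new data are needed, and competing-risks routines exist in the named software. The drawback is that the subdistribution ratio is less familiar and mixes mortality with weaning, which is the reason for showing both ratios.

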3.1 Confidence intervals and p-values

The primary clinical outcome will be tested for superiority. Other secondary outcomes will be tested for superiority, where testing is specified, or summarised and reported using descriptive statistics. Statistical tests will be two-sided with significance set at P<0.05 unless otherwise specified. Effect estimates will be reported with 95% confidence intervals. There will be no adjustment for multiple testing. The results of subgroup analyses will be interpreted taking into account accepted criteria for credible subgroup effects²,³.

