5.1 Outcome definitions

5.1.1 Primary clinical outcome

The primary clinical outcome is a composite of death and organ support by 30 days. Patients who have died on or before day 30 post randomisation are assigned the worst possible score of 31, and surviving patients are scored by the number of calendar days on which any type of organ support was given, starting from day 1 (the day on which the patient was randomised) up to and including day 30. Any organ support during the first 30 days will be included, regardless of whether the support was during the index PICU admission, on a ward, or during a re-admission to PICU.

5.1.2 Primary health economic outcomes - Incremental costs, quality-adjusted life years (QALYs) and net monetary benefit at 12 months

Economic costs will be calculated from patient-level resource use data captured through trial case report forms linked to PICANet, Hospital Episode Statistics, and follow-up patient questionnaire. Resource use for delivering the interventions, length of stay in PICU/HDU and acute hospital, for the index admission and any readmission before 12 months, and from use of personal health services after acute hospital discharge within 12 months post-randomisation will be measured. Appropriate unit costs data will be obtained from the NHS Payment by Results database, unit costs of health and social care (PSSRU) and from local Trust Finance Departments.

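### Duration of organ support and length of stay are tested within survival groups; among non-survivors the p-value mainly reflects how long children lived

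*SAP*

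**What the plan says.** SAP section 5.2.2 sets the analysis of two secondary outcomes. The first is the number of support days up to day 30, which the section says "will be compared between groups using a Wilcoxon rank-sum test, in patients stratified by survival status". For the second: "Length of PICU and acute hospital stay will be compared between groups using a Wilcoxon rank-sum test", again split by survival status, with medians and interquartile ranges by group.

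These are formal tests. The same section says of support by type that it is reported "but not formally tested for differences between groups", so the other comparisons are meant to be tested. Section 3.1 adds: "Statistical tests will be two-sided with significance set at P<0.05 unless otherwise specified", with no adjustment for multiple testing.

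Section 5.1.3.4 defines the secondary duration as "number of calendar days from day 1 to 30 on which any support was given". It carries no score for death. The primary outcome in section 5.1.1 does: "Patients who have died on or before day 30 post randomisation are assigned the worst possible score of 31".

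The SAP gives no caveat on the by-survival tests. It does not say at which time point survival status is taken, although section 5.1.3.2 lists mortality at four. It specifies no all-patient test of length of stay.

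**The concern.** Randomisation makes the arms comparable as a whole. It does not make survivors comparable with survivors, or non-survivors with non-survivors, once treatment can affect who dies or when.

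- **Non-survivors.** A child who dies on support stops accruing support days and bed-days at death. In this group a day of support is close to a day alive. A treatment that only postpones death then produces a significant result labelled as more organ support or a longer stay.
- **Survivors.** If one arm saves some of the sickest children, they join its survivor group and lengthen its durations.

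Reading the plan as one combined stratified rank test instead of two separate tests does not remove the problem, since it still conditions on survival. At stake is the interpretation of two secondary outcomes. For length of stay, these are the only between-arm p-values that the SAP specifies.

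**Working it through.** **Inputs from the SAP.** Section 2.3: total 2040, 10% allowance for withdrawal or refusal, 7.5% mortality assumed equal in both arms, 90% power for 120 versus 108 hours. Section 2.2: 1:1 allocation. Section 3.1: two-sided 0.05.

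**The plan's own figure.** The 2040 came from simulation on pilot data, and no SD is given, so it cannot be reproduced exactly. Evaluable patients are 2040 × 0.9 = 1836, or 918 per arm. A two-mean formula, n = 2 × (1.960 + 1.282)² × SD² / 12², returns 918 at an SD of about 79 hours. A simulated rank test with deaths ranked worst and 918 per arm gives 92% power at SD 72 hours and 87% at SD 80 hours, so 2040 is plausible. Nothing below depends on it beyond the 918.

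**Size of the groups.** Deaths per arm: 918 × 0.075 = 68.85, about 69. Survivors per arm: about 849.

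**Non-survivors.** Assumptions not in the SAP: support continues until death, time to death is exponential with mean 8 days, and mortality is equal. Let θ be the probability that a non-survivor in the delayed arm outlives one in the other arm.

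- Time to death multiplied by r: θ = r / (1 + r).
- Constant shift of s days with mean m: θ = 1 − 0.5 × exp(−s/m).
- Standard error of the Wilcoxon estimate of θ: √[(69 + 69 + 1) / (12 × 69 × 69)] = √(139 / 57132) = 0.0493.
- Rejection rate ≈ Φ[(θ − 0.5) / 0.0493 − 1.96].

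| Delay in one arm | θ | (θ − 0.5)/0.0493 | Rejection, formula | Simulation, calendar days capped at 30 |
|---|---|---|---|---|
| None | 0.500 | 0 | 5% | 5% |
| 1.25 times | 0.556 | 1.13 | 20% | 22% |
| 1.5 times | 0.600 | 2.03 | 53% | 53% |
| Constant 2 days | 0.611 | 2.24 | 61% | 60% |

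(5% in the first row counts both tails; the simulation used 4,000 trials per row.)

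The proportional rows do not depend on the 8-day mean, apart from the cap. The constant-shift row does: with a mean of 12 days, θ = 0.577 and rejection is about 34%; with 5 days, θ = 0.665 and it is about 92%. A separate simulation with a 7-day mean gave 50% at 1.5 times, with the median about 2.4 days longer in the arm that lived longer. In that same scenario the all-patient test with deaths ranked worst rejected in 5.2% of trials.

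**Survivors.** Assumptions: lognormal duration with mean 120 and SD 85 hours, counted in calendar days, no effect of treatment on duration, and a frailty that raises both death risk and duration (4,000 trials per row).

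| Mortality | Frailty log-odds of death per SD | Correlation with log duration | Rejection | Mean shift (days) |
|---|---|---|---|---|
| 7.5% vs 5% | 1.0 | 0.5 | 5.9% | 0.04 |
| 7.5% vs 5% | 1.5 | 0.8 | 7.8% | 0.08 |
| 10% vs 5% | 1.0 | 0.5 | 7.0% | 0.08 |
| 10% vs 5% | 1.0 | 0.8 | 11.1% | 0.13 |

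For scale, the design effect in section 2.3 is 12 hours, or 0.5 day. With no effect on mortality, rejection among survivors was 5 to 6%.

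**The case against.** The strongest reply has four parts.

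- **Organ support already has its all-patient test.** Scoring deaths 31 and applying the Wilcoxon test is the primary analysis (sections 5.1.1 and 5.2.1). The secondary outcome exists to separate out the duration component. This stands: the lack of an all-patient test is a fair complaint only for length of stay.
- **Rejection in non-survivors is not a false positive.** Duration among those who died truly differs in these scenarios; the error lies in reading it as harm. Mortality tests and Kaplan-Meier estimates by arm (section 5.2.2) would help a reader see this. That is correct, but a p-value labelled as organ support or length of stay invites the misreading, and the SAP adds no warning.
- **The delay is assumed.** Neither the 8-day mean nor the size of any delay is in the SAP. This stands, which is why a range is shown: about 20% at 1.25 times, not one headline near 60%.
- **Equal mortality is the planning assumption.** If treatment changes neither death nor its timing, the tests hold their level. That is so, but it is an assumption for sample size, and the trial tests mortality as an outcome.

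A reader might infer that these p-values have no valid causal reading at all. The documents and the numbers do not support that: the tests are valid under no effect on death or its timing, and nearly unbiased in survivors, about 92.5% of patients. A reader might also infer that the trial's main conclusion or its stopping rule is affected. It is not: section 2.6 uses the primary endpoint, which scores death explicitly.

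**Conclusion.** The point holds, at minor to moderate weight. Section 5.2.2 attaches p-values to comparisons within groups formed by a post-randomisation outcome. The material part is the non-survivor test, with about 69 children per arm: it rejects in about 20% of trials at 1.25 times longer time to death, about 50% at 1.5 times, and about 60% under a constant 2-day shift. These figures rest on exponential time to death with an 8-day mean, support until death and equal mortality. Without any effect on death or its timing, rejection stays near 5%.

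Selection among survivors is a lesser matter: about 6 to 8% rejection and under 0.1 day at 7.5% versus 5% mortality, and 7 to 11% at 10% versus 5% with frailty log-odds of 1.0. A stronger frailty link would raise the latter further, but a mortality gap that wide would be detected by the planned 30-day Fisher test about 98% of the time, so readers would know that the survivor groups differ. At 7.5% versus 5% that safeguard is weaker, about 56%.

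**What to change.** Change section 5.2.2 as follows.

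- **By survival status:** report medians and interquartile ranges for organ support and for PICU and hospital stay as description, without p-values and with no test in non-survivors. State the time point at which survival status is taken.
- **Length of stay:** make the formal comparison in all randomised patients with death handled explicitly. One option is time to live discharge with death as a competing event. The other is a rank test with deaths ranked worst, which fits the PICU definition in section 5.1.3.5 more easily because that definition adds up readmissions.
- **Organ support:** rely on the primary death-ranked analysis for the all-patient test, and present the by-survival durations as descriptive component results. No further test is needed.

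The cost is SAP wording and one all-patient analysis for each length-of-stay outcome, on data already collected. The downside is that the all-patient length-of-stay result mixes mortality and duration, as the primary endpoint already does; the descriptive summaries let a reader separate them.

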1.2.2 Secondary Objectives

- Incremental costs at 30 days
- Mortality at PICU discharge, 30 days, 90 days and 12 months
- Time to liberation from ventilation
- Duration of organ support
- Length of PICU and hospital stay
- Functional status at PICU discharge
- Health-related quality of life (HrQoL) at 12 months

2 Study Methods

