The health outcome for the economic evaluation will be summarised using QALYs, which unites quantity (survival) and quality of life into a single metric. To do this, HRQoL, which is measured on an index scale of 1 (equals full health) and 0 (equals death), at 12 months will be assessed using the Paediatric Quality of Life Generic Core Scales (PedsQL) and CHU-9D instruments. HRQoL data will be collected via age-appropriate Paediatric Quality of Life Generic Core Scales (PedsQL) and CHU-9D instruments. The responses to PedsQL questionnaire from eligible surviving children at 12 months will be mapped onto the Child Health Utility 9D (CHU-9D) score (Lambe et al, 2018). The responses to CHU-9D questionnaire will be converted into utility score using recommended algorithm (Stevens, 2012). QALYs will be calculated by valuing each patient's survival time by their HRQoL at 12 months according to the "area under the curve" approach. For 12-month survivors, QALYs will be calculated using the HRQoL scores at 12 months, assuming HRQoL of zero at randomisation, and a linear interpolation between randomisation and 12 months. For decedents between randomisation and 12 months, we will assume zero QALYs.

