5.1.3.6 Functional status at PICU discharge

Functional status at PICU discharge will be measured in surviving patients at the time of first discharge from PICU following randomisation, using the Paediatric Cerebral Performance Category (PCPC) and Paediatric Overall Performance Category (POPC) scales, which categorise performance on a 5 point scale from best (1) to worst (5).

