5.1.3.7 Health related quality of life at 12 months

Health-related quality of life at 12 months will be measured using the Paediatric Quality of Life Inventory (Peds-QL)32 and the Child Health Utility 9D (CHU-9D), completed by parents at twelve months post-randomisation.

The PEDS-QL instrument uses a different set of question of each age group of 1-12 months; 13-24 months; 2-4 years; 5-7 years; 8-12 years; 13+years. For each age group an overall score is calculated on a scale of 0-100 with higher scores indicating better quality of life. In infants under 2 years five subscales are defined, relating to physical functioning, physical symptoms, emotional functioning, social functioning, and cognitive functioning, and in children of 2 years and over four subscales are defined, relating to physical functional functioning, social functioning and school functioning.

CHU-9D was developed with children aged 7-17 and is designed to produce utility values for use in calculating quality adjusted life years (QALYs)

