5.5 Additional analyses

5.6 Safety

Adverse events (severe lactic acidosis, cardiac ischaemia, acute kidney injury, and seizures) and any other possibly related adverse event, are recorded from randomisation until 30 days after randomisation or discharge from PICU, whichever is later

The percentage of patients experiencing one or more adverse event will be compared between groups using Fisher's exact test. Counts and percentages of adverse events, and serious adverse events, overall and by type, will be presented by allocated treatment group. Safety results will be reported for the ITT and PP populations.

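### PCPC and POPC are only tabulated in survivors and the 12-month PedsQL/CHU-9D scores have no analysis in SAP 5.2.2, so no planned between-arm estimate isolates function

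*SAP*

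**What the plan says.** Section 1.2.2 of the SAP lists functional status at PICU discharge and "Health-related quality of life (HrQoL) at 12 months" as secondary objectives.

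- **PCPC and POPC, definition (5.1.3.6).** "Functional status at PICU discharge will be measured in surviving patients at the time of first discharge from PICU following randomisation". Both are five-point scales from best to worst, with no point for death.
- **PCPC and POPC, analysis (5.2.2).** "Functional status at PICU discharge will be reported as counts and percentages in each of five possible categories". That sentence is the whole analysis.
- **PedsQL and CHU-9D, definition (5.1.3.7).** "For each age group an overall score is calculated on a scale of 0-100 with higher scores indicating better quality of life". CHU-9D is described as a source of utility values.
- **PedsQL and CHU-9D, analysis.** Section 5.2.2 mentions neither. In 5.1.2, "The responses to PedsQL questionnaire from eligible surviving children at 12 months will be mapped onto the Child Health Utility 9D (CHU-9D) score", and the utility is turned into QALYs with zero for children who die. Section 5.3 reports incremental QALYs with a 95% confidence interval.
- **General rule (3.1).** Secondary outcomes are tested where a test is specified and otherwise described. There is no multiplicity adjustment.
- **Safety (5.6).** The named adverse events are "severe lactic acidosis, cardiac ischaemia, acute kidney injury, and seizures". Fisher's exact test is specified for having any adverse event. Individual types are only counted by group.

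**The concern.** Section 1.2 sets out to weigh the risks of raising SpO2 to the higher target against the benefits. If the lower target shortens organ support, a reader will next ask whether the children leave PICU, or live a year later, with worse function. The trial collects the data to answer this, but the plan yields two columns of percentages for PCPC and POPC and nothing for PedsQL as a score. No estimate would show how large a difference is, or how large a difference can be excluded.

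Two features add to this. First, percentages among survivors depend on who survives, so an arm with more deaths can show a better-looking table. The SAP deals with this elsewhere: death ranks worst in the primary outcome, and organ-support duration and length of stay are stratified by survival status. Functional status is simply restricted to survivors. Second, under 2.7 the main analysis follows day-30 follow-up and the long-term outcomes come in a later update. With no method written for PedsQL, one could be chosen after the day-30 comparison is known.

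**Working it through.** The SAP states no figure for PCPC, POPC or PedsQL, so there is none to reproduce. The text settles the main point, and the arithmetic only shows what an estimate could offer.

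**1. What each planned analysis can show about function.**
- PCPC/POPC counts: survivors only, with no effect measure or interval.
- Mortality at PICU discharge (Fisher's exact test, logistic regression if events allow): deaths only.
- Incremental QALYs: under 5.1.2 quality of life rises linearly from zero at randomisation to the 12-month utility *u*. A survivor's QALY is therefore 1 year × *u*/2 and a death scores 0. The between-arm difference is half the difference in mean 12-month utility with death at zero. This is a genuine between-arm estimate with an interval, but it mixes survival with quality of life.
- Any adverse event: pools seizures with all other events.

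None of these isolates function.

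**2. Inputs.** From 2.3: 2040 randomised, 10% lost to withdrawal or refusal, 7.5% mortality. Analysed: 2040 × 0.90 = 1836, or 918 per arm. Survivors per arm: 918 × 0.925 ≈ 849; deaths ≈ 69. The 7.5% is the design figure for day 30, and using it at PICU discharge is an assumption.

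**3. Ordinal model with death as sixth category.** Whitehead's variance: SE(log OR) = √[12 / (N(1 − Σp̄³))], where p̄ is the category proportion averaged over arms. Assume survivors at 60/20/10/7/3% in categories 1 to 5 and an odds ratio of 1.3.
- Σp̄³ ≈ 0.151, so SE = √[12 / (1836 × 0.849)] ≈ 0.088.
- The 95% CI factor is exp(1.96 × 0.088) ≈ 1.19.
- Power = Φ(ln 1.3/0.088 − 1.96) ≈ 85%.
- Category 4 or worse, including death: 16.8% versus 20.7%.

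Other assumed survivor distributions at the same odds ratio:

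| Categories 1–5 (%) | Power | CI factor |
|---|---|---|
| 40/30/15/10/5 | 88% | 1.18 |
| 60/20/10/7/3 | 85% | 1.19 |
| 80/10/5/3/2 | 73% | 1.22 |
| 90/5/3/1/1 | 60% | 1.26 |

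**4. Survivor-only table.** With the 60/20/10/7/3% distribution, categories 4–5 hold 0.10 × 92.5 = 9.25% of all children. Suppose one arm has 2 points more deaths, all from those categories. Survivors in categories 4–5 become 7.25/90.5 = 8.0%, against 9.25/92.5 = 10.0% in the other arm. With 3 points more, 6.25/89.5 = 7.0%. Category 4 or worse including death is 9.25 + 7.5 = 16.75% in both arms. This is an extreme case chosen to show the direction of the effect.

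**5. PedsQL.** Half-width of the 95% CI for a mean difference = 1.96 × SD × √(2/n), with n = 849 × response rate. Assuming 30–70% response and an SD of 15–25 points, it runs from 1.7 (70%, SD 15) to 4.3 points (30%, SD 25).

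**6. Time point of death.** Section 5.1.3.2 counts deaths until discharge to care below Level 2, whereas 5.1.3.6 scores function at first PICU discharge. A child who moves to high dependency care and dies there could be scored for function and also counted as dead. A death category must follow the second time point.

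**The case against.** The other side has a good case on several points.

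- **PedsQL does reach a between-arm estimate.** A reader might infer that it has none. That is not so: incremental QALYs are covariate-adjusted, use multiple imputation and carry a 95% CI. They are reported separately from costs, so cost weighting does not hide them. Including deaths in the scale is also what is asked for here with PCPC and POPC. This stands. What remains is that the QALY does not separate function from survival.
- **Descriptive reporting is allowed.** Section 3.1 says so, and 5.2.2 applies it openly to functional status. This stands, and there is no internal contradiction.
- **Counts are informative.** Full category counts, if tabulated by arm, allow an unadjusted odds ratio to be worked out, and PICU mortality in the same section would reveal an excess of deaths. This stands too. The sentence in 5.2.2 does not say that counts are by group, though no other reading makes sense in a two-arm comparison.
- **The harm framing is an inference.** The SAP does not say that its adverse events stand for reduced oxygen delivery, or call PCPC and POPC harm measures. The point does not need that reading, since both are listed secondary objectives.
- **The numbers are hypothetical.** They are, which is why a range is shown.

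**Conclusion.** The point holds as a cheap improvement to a permitted but weak choice. PCPC and POPC have no planned effect estimate, interval or category for death, and the PedsQL and CHU-9D scores have no analysis in 5.2.2 despite being a stated objective. The PedsQL part alone would be mostly missing detail. The stronger part is replacing bare survivor counts with a method that the SAP already uses for its primary outcome.

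A reader might go further and conclude that the trial cannot say whether the lower target worsens function. The SAP does not support that: the counts permit a crude comparison, and the QALY carries a health-status estimate with death included. The primary analysis is unaffected.

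The size is illustrative only. Power of about 60% to 88% at an odds ratio of 1.3, and CI factors of about 1.18 to 1.26, rest on assumed category distributions, proportional odds, 1836 children analysed and 7.5% mortality by PICU discharge. Even the least favourable distribution tried gives a usable bound on a difference in function.

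**What to change.** In 5.2.2, keep the PCPC and POPC counts, stated as by arm, and add wording such as:

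> PCPC and POPC will each be compared between arms by ordered logistic regression, with death before first PICU discharge as a sixth and worst category. Unadjusted odds ratios, and odds ratios adjusted for the variables in 5.2.1, will be reported with 95% confidence intervals as secondary estimates.
>
> The PedsQL total score at 12 months in survivors will be reported as an adjusted mean difference with 95% confidence interval, beside 12-month mortality and incremental QALYs.

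Tie the death category to first PICU discharge as in 5.1.3.6, not to the mortality definition in 5.1.3.2, so that no child is both scored and counted as dead. Because PedsQL questions differ by age group, the PedsQL version is a sensible extra covariate. The PedsQL difference remains a survivor comparison and should be read with the mortality and QALY results beside it.

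The cost is a few sentences and a few models on data already collected. The downside is a handful of further secondary estimates without multiplicity adjustment, which 3.1 already accepts.
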